## **List of Abbreviations**

**IBC – International Biophysics Corporation**

**HFCWO – High Frequency Chest Wall Oscillation**

**FEV1 – Forced Expiratory Volume is the volume (L) of air measured in the first one (1) second of the FVC test**

**FVC – Forced Vital Capacity shows the volume (L) of air a person can forcefully and quickly exhale after taking a deep breath**

**PEF – Peak Expiratory Flow shows the maximum airflow (L/min) during a forced expiration beginning with the lungs fully inflated**

**TV – Tidal Volume describes the volume (L) representing the normal volume of air displaced between normal inhalation and exhalation when extra effort is not applied**

**FEF25 – 75% - The mean forced expiratory flow (L/s) over the interval from 25% to 75% remaining of the Forced Vital Capacity**

## STUDY SUMMARY

Title	AffloVest Comparative Study for Air Flow in the Lungs
Protocol Number	2018-02
Phase	Device, Phase I
Methodology	
The study will be broken into one (1) arm:
 
 
- AffloVest® & Monarch™
 
 
Within each arm, the order of products will be also randomized.
 
Baseline spirometry (FEV1, FVC, PEF, FEF25-75% and TV) will be taken at the beginning, middle and end of each subject trial without any device on the subject.
 
A product (AffloVest or Monarch vest) will be placed onto subject and turned ON to the highest frequency and intensity settings, then the subject will be given a certain period. The spirometry measurements will then be repeated. The product will be removed and the subject allowed a recovery period, then the other product will be placed on the subject, turned ON and spirometry measurements repeated. A short questionnaire will also be included.

Study Duration	Approximately one (1) month
Study Center(s)	Pulmonary Disease Specialists, PA (d/b/a PDS Research) [name]
Objectives	Investigate impact of high-frequency chest wall oscillation therapy on spirometry values (FEV1, FVC, PEF, FEF25-75% and TV) during use of different products and comparing to baseline values to determine any significant variation in air flow in the lungs.
Number of subjects	10
Main Inclusion and Exclusion Criteria	
Inclusion: Healthy subject, ages 18 – 50
 
Exclusion: Non-ambulatory, diagnosed neuromuscular disorder, currently using any type of oscillation vest therapy, diagnosed co-morbid condition (i.e. lung cancer, other lung disorder or disease), currently enrolled in a medical research study, non-English speaking, presence of the following active implantable devices: pacemakers, neurostimulators, infusion pumps, circulatory support devices, implantable cardioverter defibrillators (ICD's), cochlear implants, presence of head and/or neck injury that has not yet been stabilized, presence of active hemorrhage with hemodynamic instability

Study product, Dose, Route, Regimen	
The International Biophysics AffloVest® and Hill-Rom Monarch™ will be included in the study.
 
Each subject will be properly fitted with a product and then the product will be turned ON. The subject will wear the product for a brief time before taking spirometry readings. The subject will then switch to a different product after a recovery period and the procedure will be repeated. Each subject will then be asked to fill out a short questionnaire.

Duration of subjects participation	One (1) day, approximately two (2) hours per subject

## 1 Introduction

This document is a clinical research protocol and the study will be conducted in accordance with this protocol. The study will be conducted in accordance with Good Clinical Practice Standards and all applicable regulatory requirements.

### 1.1 Background

High Frequency Chest Wall Oscillation (HFCWO) is a therapy that has been proven to be effective for many years and is used for airway clearance for patients that have difficulty mobilizing secretions in the lungs. One method to accomplish HFCWO therapy utilizes air bladder compression of the torso to create oscillation in the lungs. Air bladder companies claim “The assumption is that the effectiveness of the treatment can be measured in the mouth airflow which is believed to be the indicator of the efficacy of the therapy”. Air bladder devices claim that they create air shearing forces in the lungs by increasing air flow in the lungs by shaking and compressing the entire torso to supposedly generate airflow in the lungs to mobilize secretions. Moreover, air bladder companies have claimed that they create more air flow in the lungs than the newer oscillation technology. The purpose of this study is to measure and compare airflow actually in the lungs while using two different motorized oscillation HFCWO technologies to determine the actual air flow in the lungs. Lung airflow will be measured using standard pulmonary spirometry clinical equipment. The results will be collected and analyzed.

### 1.2 Investigational/Study Product

The devices under study are all High-Frequency Chest Wall Oscillation (HFCWO) devices which are summarized in the following table. All these devices are Class II medical devices in the USA with 510(k) clearance from FDA.

**Table 1 – Study Product**

Manufacturer and Brand	510(k) Number	Indications for Use
International Biophysics Corporation AffloVest	K122480	“The International Biophysics Corporation AffloVest is intended for promoting airway clearance and improvement of bronchial drainage by enhancing mobilization of bronchial secretions where external manipulation of the thorax is the physician’s choice of treatment”
Hill-Rom Monarch	K163378	The Monarch Airway Clearance System is intended to provide Airway Clearance Therapy and promote bronchial drainage where external manipulation of the thorax is the physician’s choice of treatment. It is indicated for patients having difficulty with secretion clearance, or the presence of atelectasis caused by mucus plugging. The Monarch Airway Clearance System is intended to be used in the Home Care environment by patients, 15 years and older.

The devices are similar in intended use, with similar modes of operation. Both products utilize mechanical oscillation of the chest wall to mobilize secretions.

Patients are prescribed these types product by a physician, along with the treatment regimen.

### 1.3 Preclinical Data

 Warwick et al 1991 Pediatric Pulmonology

 Analysis of High Frequency Chest Compression Devices and Modeling. A DISSERTATION SUBMITTED TO THE FACULTY OF THE GRADUATE SCHOOL OF THE UNIVERSITY OF MINNESOTA BY Yong Wan Lee IN PARTIAL FULFILLMENT OF THE REQUIREMENTS FOR THE DEGREE OF DOCTOR OF PHILOSOPHY/ELETRICAL ENGINEERING Bruce F. Wollenberg, Thomas J. O’Dea December 2007

 Independent lab testing analyzed and compared average airflows at the mouth generated by high frequency chest wall oscillation (HFCWO) therapy in 10 subjects using home care garments Airflows measured at commonly prescribed medium pressures (50% of maximum) at multiple therapy frequencies (5, 10, 15, and 20 Hz). Test data and reports on file at Hill-Rom, Inc

Preclinical studies of the AffloVest product have been performed by IBC to demonstrate substantial equivalence of the device to other similar devices (predicates). The preclinical studies including electrical safety and EMC testing, testing for compliance with home-healthcare standards for electrically powered devices, human factors and usability testing, software validation and system verification testing.

Preclinical data has been gathered by the other products but is confidential to those manufacturers. A summary of the preclinical test data is included in the 510(k) summary for each device.

Preclinical data regarding these devices is not expected to have clinical significance nor relevance to this trial.

#### **1.4 Clinical Data to Date**

There is no clinical data to date regarding the spirometry measurements to be taken in this study.

There are no known potential risks to subjects using the AffloVest. The product has been marketed since 2014 with zero (0) adverse events reported in that timeframe.

IBC does not have any adverse event data on the competitor products, but these types of devices are widely regarded as safe.

The study provides no foreseeable benefits to the subjects.

#### **1.5 Dose Rationale**

These devices are typically prescribed to be used daily for 20 – 30 minutes one (1) or two (2) times daily at home.

The devices settings have been specified as the highest intensity and frequency for each device to ensure consistency across all devices. The approach taken will simulate spirometry values for patients during normal use of these products.

#### **1.6 Risk/Benefits**

This study poses no foreseeable risk to the subjects. The study provides no foreseeable benefits to the subject. These devices are generally considered safe with low incidence of adverse events in normal use. The study activities are not expected to impart greater than minimal risk to the subjects.

All data collected will remain confidential. Only the investigators involved with this study will have access to it. In order to maintain confidentiality, all records will be kept in locked filing cabinet(s) at the investigator site(s). If the results of the study are published, the data will be reported collectively without mention of any subject's identity, thereby ensuring subject anonymity.

## **2 Study Objectives**

The purpose of this trial is to investigate the potential relationship between the use of common HFCWO devices to measure air flow in the lungs in healthy subjects using standard spirometry techniques.

## **3 Study Design**

### **3.1 General Design**

This pilot study has been designed as follows:

- One (1) arm
- This is a pilot investigational study, based on the study design there are no blinding or randomization measures taken. It is expected that the degree of bias shall be low based on the subjective endpoints under study. Each subject shall serve as their own control as

baseline spirometry measurements will be performed at the beginning and end of the visit.

- Each subject will participate for a period of approximately two (2) hours.
- There is no subject follow-up, all measurements will be performed within the initial subject visit. At the end of the visit, each subject shall be required to complete a brief survey regarding their experience.

### **3.2 Primary/Secondary Endpoints**

The following primary and secondary endpoints are to be analyzed in the study:

Primary endpoints:

1. Difference in spirometry measurements (FEV1, FVC, PEF, FEF25-75% and TV) between the AffloVest device and Monarch devices.

Secondary endpoints:

1. Survey results using a Likert scale related to:
  - a. Subject opinion on using each device on a daily basis
  - b. Subject opinion on lifestyle fit for each device
  - c. Subject opinion on lifestyle obtrusiveness of each device
  - d. Subject opinion on mobility during use of each device
  - e. Subject opinion on noise level of each device
  - f. Subject opinion on compliance with treatment of each device

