### 5.2 Treatment/Dosing Regimen

Each subject shall perform the following regimen:

1. Pre-baseline spirometry measurements (without device on patient)
2. Placement of either AffloVest or Monarch on subject, turn device ON, allow subject to acclimate to device for five (5) minutes
  - a. Repeat spirometry measurements
3. Remove device from subject and allow subject to recover for fifteen (15) minutes
4. Interim-baseline spirometry measurements (without device on patient)
5. Placement of other product (either AffloVest or Monarch, whichever was not used previously) on subject, turn device ON, allow subject to acclimate to device for five (5) minutes
  - a. Repeat spirometry measurements
6. Remove device from subject and allow subject to recover for fifteen (15) minutes
7. Post-baseline spirometry measurements (without device on patient)

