## **7 Statistical Procedures**

### **7.1 Sample Size Determination**

This is a pilot investigational trial. No statistical analysis was performed in the generation of the sample size, however similar studies for these types of devices were reviewed to determine an adequate sample size.

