### **7.2 Statistical Methods**

The metrics for the study shall be calculated as follows:

- Subject baseline values: An average of the pre-baseline, interim-baseline and post-baseline measurements shall be taken for FEV1, FVC, PEF, FEF25-75% and TV for each subject
- Comparison of the subject baseline values will be made with their values while using each device. A Student's t-test will be used to look for statistically significant differences at the 95% confidence level

Any deviation(s) from the original statistical plan shall be communicated to the IRB and the protocol shall be revised, if required.

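### The primary endpoint is the AffloVest-Monarch difference, but section 7.2 tests each device only against averaged baseline, so the primary endpoint is never tested

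*Combined protocol and SAP*

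**What the plan says.** - **Purpose.** Section 1.1: "The purpose of this study is to measure and compare airflow actually in the lungs while using two different motorized oscillation HFCWO technologies".
- **Primary endpoint.** Section 3.2: "Difference in spirometry measurements (FEV1, FVC, PEF, FEF25-75% and TV) between the AffloVest device and Monarch devices". The five measures have equal standing and none is named as lead.
- **Analysis.** Section 7.2 averages the pre-, interim- and post-baseline values for each subject and measure, then states: "Comparison of the subject baseline values will be made with their values while using each device". On significance, the section names only Student's t and says that it "will be used to look for statistically significant differences at the 95% confidence level". It does not state pairing, sidedness, a multiplicity rule or a success rule.
- **Objective.** The Study Summary also frames the aim against baseline: "comparing to baseline values to determine any significant variation in air flow in the lungs".
- **Design.** Ten subjects each use both devices. Section 5.2, second period: "Placement of other product (either AffloVest or Monarch, whichever was not used previously) on subject". Section 3.1 makes each subject their own control, and section 5.3 alternates device order, five subjects per order.
- **Status.** Section 7.1: "This is a pilot investigational trial". The sample size has no statistical derivation.

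**The concern.** The endpoint in 3.2 is a contrast between two devices. The tests in 7.2 are contrasts of each device with no device, which answer a different question. AffloVest can differ significantly from baseline while Monarch does not, or the reverse, without any evidence that the two differ from each other.

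The study exists to compare the two products, so a results table of device-versus-baseline p-values is likely to be read as that comparison. With 10 subjects, whether a given device crosses the 5% line is partly chance, and a split result is an ordinary outcome even for equally effective devices.

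A second, smaller issue follows. Once the missing between-device test is supplied, there are five of them, and nothing says which one decides.

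**Working it through.** **1. Figures in the plan.** The only design figure is N = 10, given without a calculation, so there is nothing to reproduce. The documents give no effect size, SD, correlation or power. Tests below are taken as two-sided at 0.05, because sidedness is not stated.

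**2. The data suffice for the right test.** For subject *i* and one measure, let A, M and B be the AffloVest value, the Monarch value and the averaged baseline. Then (A − B) − (M − B) = A − M. The baseline cancels, so the primary contrast needs only the two on-device readings already planned in 5.2.

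**3. How misleading is one device significant and the other not?** Model for one measure: five occasions per subject (three baselines, two devices), independent errors with variance σ², the same true effect for both devices, and no subject-by-device variation.
- Var(A − B) = σ²(1 + 1/3) = 1.33σ².
- Cov(A − B, M − B) = σ²/3, so the two baseline contrasts correlate at (1/3)/(4/3) = 0.25.
- Simulation, n = 10, 200,000 trials per setting, effect in SDs of A − B:

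| Common true effect | Each device significant vs baseline | Exactly one significant | Direct paired A − M test significant |
|---|---|---|---|
| 0.5 SD | 29% | 36% | 5% |
| 0.7 SD | 50% | 43% | 5% |
| 1.0 SD | 80% | 28% | 5% |

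As a rough check, two independent tests with power *p* would split with probability 2*p*(1 − *p*): 0.32 at *p* = 0.80 and 0.50 at *p* = 0.50. The shared baseline lowers these to 0.28 and 0.43. The split rate is smaller outside this range of effects: 9% with no effect and 11% at 1.25 SD.

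**4. Multiplicity if the gap is filled with five paired tests.** Under no device difference and independence, 1 − 0.95⁵ = 0.226. Simulated chance of at least one p < 0.05 (n = 10, 9 df) by assumed correlation between the within-subject device differences:
- Common correlation 0 / 0.5 / 0.7 / 0.9 / 0.95: about 23% / 19% / 16% / 11% / 9%.
- Four forced-expiration measures at 0.7-0.9, tidal volume (TV) at 0-0.3 with them: 14-18%.
- Four forced measures at 0.3-0.5, TV at 0-0.3: about 20-22%.

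The List of Abbreviations defines FEV1 as "Forced Expiratory Volume is the volume (L) of air measured in the first one (1) second of the FVC test", so full independence is unlikely. That overlap does not fix the correlation between device *differences*, which is what matters here, so the whole 9-23% range should be shown.

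**5. Precision available.** The half-width of a 95% interval for a paired mean difference is t(0.975, 9)/√10 = 2.262/3.162 = 0.72 SD of the within-subject difference.

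**The case against.** **It is a pilot, with all five measures named in advance and no overall error rate claimed.** This stands, and it keeps the multiplicity point small. It does not excuse the mismatch: 7.2 still looks for significance, and a pilot should say which test answers its primary endpoint.

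**A reader might infer that the plan carries a false-positive rate of 14-18%.** The documents do not support that. The figure belongs to five tests that 7.2 does not contain, and to one choice of correlations. The ten baseline tests that 7.2 does describe would give at least one false positive in about 25-40% of trials if neither device had any effect (correlation between measures 0.8 down to 0). Those tests do not address the primary endpoint either.

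**A reader might infer that pairing is open and that an unpaired test would lose much of the power.** The word paired is indeed missing. But section 3.1 makes each subject their own control, and 7.2 compares each subject's baseline with that same subject's device values. The text points to a within-subject analysis, so only a wording repair is needed.

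**A reader might infer that everything may be chosen freely after the data are seen.** Section 7.2 requires deviations from the statistical plan to go to the IRB, with protocol revision if required. That is some control, but it does not supply the missing test.

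**A single lead measure is not obligatory.** Agreed. With no success rule in a 10-subject pilot, labelling all five exploratory is an equally sound choice.

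**Conclusion.** The concern holds as a mismatch between endpoint and analysis. That the primary contrast in 3.2 has no test in 7.2 is evident from the text and needs no assumption.

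The cost of substituting the baseline tests is material: for equally effective devices, a misleading split in 28-43% of trials at true effects of 0.5-1.0 SD, against 5% for the direct test. Those figures are per measure and rest on independent errors between occasions and no subject-by-device variation.

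Multiplicity is secondary. It is 9-23% across assumed correlations of 0.95 to 0, and only if the gap is filled with five unadjusted paired tests. The plan should be corrected before data are seen. Nothing here shows that the design or the data collection is unfit for the comparison.

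**What to change.** In section 7.2, replace the present comparison with wording such as:

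*The primary analysis is the within-subject AffloVest-minus-Monarch difference for each spirometry measure, by two-sided paired t-test at the 5% level. Mean differences with 95% confidence intervals will be reported for all five measures, whatever their p-values. Comparisons of each device with the averaged baseline are supportive, and are reported as paired mean differences with 95% confidence intervals.*

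Then:
- **Lead measure.** Either name one in 3.2 before data are seen, with the other four exploratory, or label all five exploratory. Holm across five is possible but expensive: for a true difference of 1.00 SD of the within-subject difference, power at its first step (0.05/5 = 0.01) is 50%, against 80% at 0.05.
- **Device order (optional).** Allow for the order alternated in 5.3. A 5/5 split balances a period effect in the mean, but an unmodelled one still adds to the SD. Section 4.4 does not say which order a replacement subject receives, so the balance could be lost.
- **Study Summary objective.** Align it so that the between-device comparison is primary and change from baseline is supportive.

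**Cost.** Wording in the Study Summary, 3.2 and 7.2, and a little analysis; no added subjects, visits or measurements. The downside is that measures not named as lead, and the baseline comparisons, no longer support a stand-alone significance claim. Each would be read from its interval, about ±0.72 SD of the relevant within-subject difference at n = 10.

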## **4 Subject Selection and Withdrawal**

### **4.1 Inclusion Criteria**

The following subjects shall be eligible for study enrollment:

1. Healthy subject, ages 18 – 50

### **4.2 Exclusion Criteria**

The following subjects shall be ineligible for study enrollment:

1. Non-ambulatory
2. Diagnosed neuromuscular disorder
3. Currently using any type of oscillation vest therapy
4. Diagnosed co-morbid condition (i.e. lung cancer, other lung disorder or disease)
5. Currently enrolled in a medical research study
6. Non-English speaking
7. Presence of the following active implantable devices:
  - a. Pacemakers
  - b. Neurostimulators
  - c. Infusion pumps
  - d. Circulatory support devices
  - e. Implantable cardioverter defibrillators (ICD's)
  - f. Cochlear implants
8. Head and/or neck injury that has not yet been stabilized.
9. Active hemorrhage with hemodynamic instability

### **4.3 Subject Recruitment and Screening**

Subjects will be recruited in accordance with the investigator standard operating procedure (SOP) for subject recruitment.

Based on the small number of subjects required and short study duration, it is expected that the following methods will be used for subject recruitment:

- Internet/company website
- Private practice database

Subjects will be screened by the investigator according to the standard operating procedure (SOP) in place at the investigator's site.

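### The eligibility criteria do not exclude people tied to either manufacturer or the site, although subjects rate both vests unblinded (minor)

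*Combined protocol and SAP*

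**What the plan says.** - **Recruitment (Section 4.3).** The expected channels are "Internet/company website" and "Private practice database", under the investigator's recruitment procedure. Whose company is meant is not stated. On screening: "Subjects will be screened by the investigator according to the standard operating procedure (SOP) in place at the investigator's site". Neither procedure is reproduced.
- **Eligibility (Sections 4.1 and 4.2).** The single inclusion criterion is "Healthy subject, ages 18 – 50". Of the nine exclusions, the only one on vest exposure is "Currently using any type of oscillation vest therapy". Two others matter here: "Diagnosed neuromuscular disorder" and "Diagnosed co-morbid condition (i.e. lung cancer, other lung disorder or disease". None concerns affiliation with a manufacturer or the site.
- **Blinding (Sections 3.1 and 8.4).** There is none. Section 3.1 nevertheless expects little bias, and gives the subjective endpoints as its reason.
- **Endpoints (Section 3.2).** The primary endpoint is the spirometry difference between the two vests. The secondary endpoint is "Survey results using a Likert scale related to" six opinions on each device: daily use, lifestyle fit, obtrusiveness, mobility, noise and compliance.
- **Data collected (Section 6, Phase 1).** Demographics, height, weight and comorbidities. Employer, affiliation and recruitment source are not listed.

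**The concern.** The trial compares the vest made by International Biophysics Corporation, whose role as sponsor follows from Sections 1.3, 8.2 and 8.7, with a competitor's vest. Section 1.1 disputes airflow claims made by air-bladder companies, so the result has commercial weight. Someone who works for one of the makers or for the site, or is related to someone who does, may prefer one product before putting it on.

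Such a preference can act directly on the survey, because every secondary endpoint is the subject's own opinion. It could also act on spirometry. FEV1, FVC, PEF and FEF25-75% come from a forced expiration, as the List of Abbreviations indicates, so they depend on effort; tidal volume does not in the same way.

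The alternating order in Section 5.3 is meant to balance the effect of which device comes first. A preference attached to the product has the same sign in both orders, so averaging over the orders leaves it in place. In a sample of ten, one or two such subjects carry visible weight.

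**Working it through.** No figure in the plan depends on this point, so there is nothing to reproduce. The check is a reading of the text, followed by arithmetic on assumed inputs.

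**Step 1: does any criterion bar an affiliated person?** Take a healthy 30-year-old employee of the sponsor or the site who speaks English, walks unaided, has none of the listed diagnoses, implants or injuries, is in no other study and is not using a vest. This person meets Section 4.1 and none of the nine items in Section 4.2, and is therefore eligible on the protocol's own text.

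**Step 2: would the data show it afterwards?** The Phase 1 items in Section 6 do not include affiliation, and the source documents in Section 9.2 are the spirometry data and the survey. An affiliated subject could not be picked out for a sensitivity analysis.

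**Step 3: how far can a few subjects move a mean?** From the documents: n = 10 (Study Summary). Assumed: k affected subjects, each with a rating difference (one vest minus the other) shifted by s points towards the same vest. The length of the Likert scale is not given.

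Shift in the mean difference = k × s / 10

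| k | s = 1 | s = 2 | s = 4 |
|---|---|---|---|
| 1 | 0.1 | 0.2 | 0.4 |
| 2 | 0.2 | 0.4 | 0.8 |
| 3 | 0.3 | 0.6 | 1.2 |

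This is arithmetic on a mean and does not depend on any test.

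**Step 4: how likely is at least one affected subject?** If a share p of recruits were affected (assumed; the documents give no basis for p), the chance is 1 − (1 − p)^10:

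- p = 5%: 1 − 0.95^10 = 40%
- p = 10%: 1 − 0.90^10 = 65%
- p = 20%: 1 − 0.80^10 = 89%

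**Step 5: what would a significance test do?** This is illustrative only. Section 7.2 assigns Student's t-test to the spirometry comparison with baseline and names no test for the survey. Suppose a paired t-test (two-sided 5%) were applied to ten normally distributed rating differences with no true device difference and an assumed SD of 1.0 or 1.5 points. In 200,000 simulated trials per setting, the rate of significant results favouring the preferred vest was:

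| k | s = 1, SD 1.0 / 1.5 | s = 2, SD 1.0 / 1.5 |
|---|---|---|
| 0 | 2.5% / 2.5% | 2.5% / 2.5% |
| 1 | 4.0% / 3.5% | 4.3% / 4.2% |
| 2 | 6.2% / 5.0% | 8.4% / 7.2% |
| 3 | 9.7% / 6.9% | 16.2% / 12.3% |

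With one affected subject the effect is small. It becomes appreciable only if two or three of the ten are affected and all lean the same way.

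**Step 6: former vest users.** Section 1.1 describes the therapy as one for patients who have difficulty mobilising secretions, and Section 1.2 says the devices are prescribed by a physician. The healthy-subject rule and exclusions 2 and 4 therefore remove most people who were ever prescribed a vest. What remains is a small group, such as a healthy person who once tried a vest in a demonstration or an earlier study.

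**The case against.** The strongest reply is that the documents show no actual bias and no plan to enrol affiliated people. Several parts of it stand.

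- **The website.** A reader might infer from "Internet/company website" that the sponsor will recruit its own staff. The text does not support this. The phrase sits under the investigator's procedure, next to the practice's own database, and the study centre is itself a company, so its own site is a natural reading. A web notice also reaches the public. Affiliated people could enter because no criterion bars them, whichever website is used.
- **The unseen procedures.** A rule against enrolling staff or relatives may sit in the site's procedure. That is possible, but the protocol neither states nor requires one, and its reader cannot check.
- **Former users.** A reader might infer that anyone who used either vest in the past can enter. The health criterion and exclusions 2 and 4 remove most of them.
- **The simulated rates.** A reader might take the 7–16% for two or three affected subjects at a 2-point shift as the trial's false-positive rate. They are not: the number affected, the shift, its common direction and the SD are all assumed, and the plan gives no survey test.
- **The endpoint.** The survey is secondary. An effect on the primary spirometry endpoint is plausible, but nothing in the documents allows it to be sized.
- **The setting.** Section 7.1 calls this a pilot, with no statistical calculation behind the sample size.

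These replies limit how much the point matters. They do not close the gap: the enrolment rules are silent on affiliation, and the lack of blinding leaves the ratings open to it. Section 3.1's reassurance does not help, since subjective endpoints without blinding are more open to such bias, not less.

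**Conclusion.** The concern holds in a limited form. The written criteria allow people with a tie to either manufacturer or to the site to take part in an unblinded comparison of the two products, and the planned data would not identify them. Whether any will take part cannot be told from the documents.

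The firm part of the size is that each affected subject contributes one tenth of his or her shift to the mean: 0.2 points for an assumed 2-point shift. How many subjects would be affected, and by how much, is unknown. Past vest use is a small residual matter. Not saying whose website is used is missing detail, not evidence of bias. Severity is minor; the reason to act is that the remedy is nearly free and no analysis can supply it later.

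**What to change.** Add one exclusion to Section 4.2, and to the matching list in the Study Summary: *Employee, contractor or immediate family member of the sponsor, of the other device's manufacturer or of the study site.* It should be in place before the first subject is enrolled. If the site's procedure already contains such a rule, the line simply makes it visible.

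Optionally, also exclude previous use of either study vest. This is a small addition, given how few such people the other criteria leave.

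The cost is one or two lines of text, a question at screening, and a slightly smaller pool from which to find ten healthy adults. The analysis does not change.
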